8 STATISTICAL PLAN

This section contains a brief overview of the statistical analyses planned for this study. A formal pharmacokinetic analysis plan, providing full technical details, will be finalized prior to database lock.

8.1 Sample Size

The current study will be conducted in 2-parts, and the total sample size is approximately 76 patients. Phase 1 is a dose-finding study using 3+3 design to determine the MTD/MAD in each dosing group (QD or BID). Up to 18 patients (up to 3 dose levels, up to 6 patients each level) will be included for DLT evaluation in each dosing group for a total of 36 patients in Phase 1. Patients who discontinue from the study before completing Cycle 1 treatment for reasons other than DLTs are not qualified for DLT evaluation and will be replaced.

Once the dose and regimen are identified, patients will be enrolled into Phase 2 to confirm the safety and evaluate the preliminary efficacy of pozotinib using the selected dose and schedule. In Phase 2, two cohorts of 20 patients each will be enrolled in previously treated NSCLC patients with EGFR Exon 20 insertion mutations and HER2 exon 20 insertion mutations respectively.

Although no a priori test of hypothesis and statistical powering is specified in this study, the statistical methods and test of comparison follows that of SPI-POZ-202, a global pivotal study. In that study, a single arm hypothesis testing to reject non-desired ORR of 17% vs. clinically meaningful ORR of 30% will be evaluated for previously treated NSCLC patients with EGFR Exon 20 insertion mutations and HER2 exon 20 insertion mutations respectively.

The above sample size of 20 patients in each mutation cohort will provide a width for 95% confidence interval of 0.424 for the expected ORR of 30%.

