The total sample size for this study is approximately 76 patients. Phase 1 is a dose finding study using “3+3” design to determine the MTD/MAD in each dosing group (QD or BID). Up to 18 patients (up to 3 dose levels, up to 6 patients each level) will be included for DLT evaluation in each dosing group for a total of 36 patients in Phase 1. Patients who discontinue from the study before completing Cycle 1 treatment for reasons other than DLTs are not qualified for DLT evaluation and will be replaced.

A total of 40 patients (20 patients each in EGFR and HER2 mutation cohorts) will be enrolled in the dose confirmatory group in Phase 2 to confirm the activity in the identified pozotinib dose and schedule. The sample size of 20 patients in each mutation cohort in Phase 2 will provide a width for 95% confidence interval of 0.424 for the expected ORR of 30%.

Efficacy Analysis:

The primary efficacy variable ORR will be analyzed descriptively along with the 95% CI for each cohort. The determination of the ORR will be based upon radiographic assessment by the site’s Principal Investigator using RECIST Version 1.1. The secondary outcomes, DCR, DoR, and PFS, will be analyzed using descriptive statistics, for each cohort, and with 95% CI for DCR and Kaplan-Meier plot for DoR and PFS.

Analysis Populations:

The following analysis populations have been defined for each cohort:

[figure not shown]
- The **Evaluable Population** consists of all patients in Phase 2 who are enrolled, complete at least 1 cycle of pozotinib treatment, and are evaluable for tumor response based on RECIST, Version 1.1 criteria. The efficacy data will be analyzed using the Evaluable Population.
- The **Safety Analysis Population** includes all patients who signed Informed Consent, enrolled, and received at least 1 dose of pozotinib. All demographics, Baseline characteristics, and safety data will be analyzed using the Safety Analysis Population.

Safety and Tolerability:

The following variables will be summarized and analyzed descriptively for each cohort: number of completed cycles; number and percentages of patients with TEAEs, SAEs, TEAEs leading to study drug discontinuation, TEAEs related to the study drug; and the severity of TEAEs based on the grading by CTCAE, Version 5.0.

[figure not shown]
Protocol Version/Date: Amendment 2/04 Mar 2020

Study Design Diagram

Note: Phase 2 will start once the dose and dosing schedule have been determined in Phase 1.

Dose-Finding Diagram

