1.2 Rationale for the Current Study

Pozotinib is an orally administered, irreversible pan-HER inhibitor with activity against HER1, (ErbB1; EGFR), HER2 (ErbB2), and HER4 (ErbB4), as well as HER receptor mutations. The clinical results and safety profile of pozotinib to date in various studies involving patients with relapsed or refractory solid tumors as either a single agent or as combination therapy, have demonstrated that pozotinib may be a good option for patients harboring these mutations. These data support the expectation that pozotinib will be efficacious and well tolerated in solid tumor patients that overexpress EGFR or HER2 or that harbor mutations in EGFR or HER2.

[figure not shown]
Doses from 0.5 mg to 32 mg for 14 days of a 21-day cycle were evaluated in a Phase 1 study (**HM-PHI-101**) in Korean patients with advanced solid tumors. Grade 3 diarrhea was reported as a DLT in one patient each in the 12-mg, 16-mg, and 24-mg dose groups. Two patients had Grade 3 diarrhea in the 32-mg group. No DLTs were reported in patients given <12 mg pozotinib. The MTD was determined to be 24 mg for intermittent dosing.

In another Phase 1 study (**HM-PHI-102**), Korean patients with advanced solid tumors were treated with doses of 12 mg, 18 mg, or 24 mg continuously for 28 days. One patient treated with 18 mg pozotinib had a DLT of Grade 3 decreased appetite. A patient treated with 24 mg pozotinib experienced two DLTs of Grade 3 diarrhea and Grade 3 decreased appetite. None of the patients treated with 12 mg pozotinib experienced DLTs and it was determined that the MTD for continuous dosing was 18 mg.

SPI-POZ-202 is an ongoing, multinational, Phase 2 study of pozotinib treatment in patients with locally advanced or metastatic lung cancer with EGFR or HER2 exon 20 insertion mutations. The starting dose for this study is 16 mg once daily. Enrollment into Cohort 1 (previously treated patients with EGFR mutations) and Cohort 2 (previously treated patients with HER2 mutations) in that study has been completed. Preliminary data from Cohort 1 for the primary endpoint (ORR) have been analyzed.

[figure not shown]

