Cohort 1 enrolled a total of 115 patients who received 16 mg/day of pozotinib. The Intent-to-Treat analysis showed that 17 patients had a response (by RECIST) and 62 patients had stable disease for a 68.7% disease control rate (DCR). The confirmed objective response rate (ORR) was 14.8% (95% CI; 8.9%-22.6%). The median duration of response was 7.4 months. The best change in target lesion dimensions from Baseline is presented in **Figure 9**. The safety profile was at the high end of expected toxicities but in-line as to type of AE with other second-generation EGFR tyrosine kinase inhibitors. Permanent drug discontinuation related to AEs was seen in only 10% of patients but temporary drug interruption was seen in 88% of patients and dose reduction was seen in 68% of patients as permitted by protocol.

Figure 9 Best Percent Change in Sum of Target Lesion Dimension from Baseline

This study is being conducted to evaluate the safety of pozotinib in Japanese patients, a dose-escalating study beginning at 8 mg pozotinib QD and 4 mg BID is being conducted. Pharmacokinetic modeling of the 8 mg BID and 16 mg QD doses (the highest potential doses in the study), shows that BID dosing decreases fluctuations (i.e., difference between peak and trough concentrations) compared to QD dosing with a lower C_{max} (Figure 10) and the predicted AUC is expected to be similar for equivalent total daily doses. In Study HM-PHI-101, the 8-mg QD dose was well-tolerated in Phase 1 patients. In addition, activity and safety of BID dosing with pozotinib has not been previously investigated.

Figure 10 Simulated Poziotinib Plasma Concentrations Following QD and BID Dosing

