8.4 General Statistical Methods

The Sponsor's Biostatistics and Data Management (BDM) group will be responsible for data management and statistical analysis of this study. All statistical analyses will be performed using SAS for Windows (version 9.3 or higher). Further details of the criteria and conduct of the statistical analyses will be included in the SAP for this study.

Descriptive statistics will be used to describe the recovery of radioactivity and PK parameters. Pharmacokinetic parameters will be computed and analyzed by standard analytical methods.

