8.5 Efficacy Analyses

Phase 1: No efficacy analyses will be performed in Phase 1.

Phase 2: The primary efficacy variables, as described below, will be summarized and analyzed descriptively, along with 95% CI, for each cohort based on local radiographic review.

- **Objective Response Rate (ORR)** will be assessed according to the Response Evaluation Criteria in Solid Tumors (RECIST) Guidelines, version 1.1 [22] and is defined as the best response [Complete Response (CR) + Partial Response (PR)] recorded from the start of the study until the end of study in patients who received at least 1 dose of pozotinib. The ORR will be based on the Evaluable Population.

The primary endpoint analysis will be performed using point estimate and the 95% CI.

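### Does Section 8.1 leave open a hypothesis test of ORR against 17% that the planned analysis does not contain?

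*Combined protocol and SAP*

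**What the plan says.** Protocol Section 8.1 (Sample Size) sets two Phase 2 cohorts of 20 patients, EGFR and HER2. It states that "no a priori test of hypothesis and statistical powering is specified in this study, the statistical methods and test of comparison follows" those of SPI-POZ-202. The next sentence, which opens by referring to that other study, describes a "single arm hypothesis testing to reject non-desired ORR of 17% vs. clinically meaningful ORR of 30"%, applied to each mutation group. The section closes by saying that 20 patients per cohort "will provide a width for 95% confidence interval of 0.424 for the expected ORR of 30"%; the synopsis gives the same figure.

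The planned analysis is stated in two places. Section 8.5: "The primary endpoint analysis will be performed using point estimate and the 95% CI". Synopsis, Efficacy Analysis: "The primary efficacy variable ORR will be analyzed descriptively along with the 95% CI for each cohort". Section 8.4 adds: "Further details of the criteria and conduct of the statistical analyses will be included in the SAP for this study".

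On earlier response data, Section 1.2 says of SPI-POZ-202: "Preliminary data from Cohort 1 for the primary endpoint (ORR) have been analyzed". Cohort 1 was previously treated EGFR patients, 115 of them, at 16 mg/day: "The confirmed objective response rate (ORR) was 14.8% (95% CI; 8.9%-22.6"%). The documents give no poziotinib response rate for HER2 exon 20 patients.

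**The concern.** One sentence of Section 8.1 both denies a hypothesis test and says that a test of comparison is carried over from a pivotal study with a stated null of 17%. The populations match, so the borrowed test could be applied directly. If it were available, an author could decide after seeing the data whether to report that a cohort had rejected 17%. In an open-label trial with investigator-assessed response, that choice should not be left open. With 20 patients such a test would also have little power.

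A second doubt attaches to the planning rate. Precision is quoted only at 30% for both cohorts, yet the one EGFR exon 20 rate reported for this drug is 14.8%. Its upper limit of 22.6% lies below 30%, and its point estimate lies below even the 17% that SPI-POZ-202 treats as undesirable.

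**Working it through.** **Inputs.** n = 20 per cohort, planning ORR 30%, 95% CI, stated width 0.424 (Section 8.1); 17% and 30% as the SPI-POZ-202 null and alternative (Section 8.1); 17 responders of 115 (Section 1.2). The documents state no alpha or sidedness for a test. One-sided 2.5% and one-sided 5% are assumed below to show the range.

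**Step 1: reproduce the plan's figure.** The exact (Clopper-Pearson) limits for x responders of n are the 2.5% quantile of Beta(x, n − x + 1) and the 97.5% quantile of Beta(x + 1, n − x). A 30% rate in 20 patients is x = 6.

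- 6/20: 11.9% to 54.3%; width 0.5428 − 0.1189 = 0.424. This matches the plan.
- The Wald width, 2 × 1.96 × √(0.3 × 0.7/20) = 0.402, does not match, so the stated figure points to the exact interval.
- 17/115 = 14.8%, exact limits 8.9% to 22.6%. This matches Section 1.2.

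**Step 2: does any statement of the analysis contain a test?**

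| Place | Content | Test for this trial? |
|---|---|---|
| 8.1, first half of the sentence | no a priori test or powering | denied |
| 8.1, second half | methods and test of comparison follow SPI-POZ-202 | loosely implied |
| 8.1, next sentence | 17% vs 30%, attributed to SPI-POZ-202 | no |
| 8.1, close | CI width at 30% | no; estimation |
| 8.5 | descriptive; point estimate and 95% CI | no |
| Synopsis | descriptive; 95% CI per cohort | no |

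Only one clause points the other way, and it brings no null, level or rule with it for this trial.

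**Step 3: if a reader compared the result with 17% anyway, would the answer depend on the reading?** The exact one-sided p-value is P(X ≥ x) for X ~ Binomial(n, 0.17). The CI excludes 17% when its lower limit is above 17%.

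- 7/20: p = 0.041; CI 15.4% to 59.2%, which includes 17%.
- 8/20: p = 0.013; lower limit 19.1%, which excludes 17%.

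Fewest responders needed to exclude 17%:

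| Evaluable n | 15 | 16 | 17 | 18 | 19 | 20 |
|---|---|---|---|---|---|---|
| 95% CI lower limit above 17% | 7 | 7 | 7 | 7 | 8 | 8 |
| Exact test, one-sided 2.5% | 7 | 7 | 7 | 7 | 8 | 8 |
| Exact test, one-sided 5% | 6 | 6 | 7 | 7 | 7 | 7 |

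At the level that matches a two-sided 95% CI, test and interval agree in every column. They differ only at one-sided 5%, a level that appears nowhere in the documents.

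**Step 4: power of the borrowed test at a true 30%, n = 20.** P(X ≥ 8 | 0.30) = 22.8% at one-sided 2.5%; P(X ≥ 7 | 0.30) = 39.2% at one-sided 5%. Neither would be chosen as a design, which fits the explicit statement that the trial is not powered for a test.

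**Step 5: does 30% overstate precision for EGFR?** At a rate near 14.8%, 20 patients give about 0.148 × 20 ≈ 3 responders. The exact interval for 3/20 is 3.2% to 37.9%, width 0.379 − 0.032 = 0.347. That is narrower than 0.424, so the figure quoted at 30% is the more cautious of the two.

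**The case for a change.** The best case for a change is grammatical. The main clause of the Section 8.1 sentence speaks of this study's methods and test, not SPI-POZ-202's, and Section 8.5 contains no test to which it could refer. Deferring detail to a SAP does not settle the matter, since whoever writes the SAP starts from the same sentence. If that author chose one-sided 5%, 7 responders of 20 would reject 17% while the reported interval included it, and exactly 7 of 20 has probability 16.4% in a cohort whose true rate is 30%.

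Some of this stands: the clause is loose, and striking the reference to a test would make the section read better. The consequence does not stand as a fault of the plan. It requires adding an alpha that the documents do not supply, setting aside the denial in the same sentence, and departing from Section 8.5 and the synopsis. The 16.4% also depends on the true rate: at 14.8%, exactly 7 of 20 has probability 1.5%.

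On the planning rate, it is fair that 30% is not an observed result. It equals SPI-POZ-202's design target for both mutation groups. The 14.8% is a preliminary, confirmed, intent-to-treat rate at 16 mg/day, whereas this trial reports best response in the Evaluable Population at a dose and schedule still to be chosen. It therefore leaves 30% without support in EGFR patients but does not disprove it. Extra rows of precision at other rates would be a presentational preference.

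**Conclusion.** No change follows. This is a loosely worded clause in a sample-size section, not a rival primary analysis. Analysts following Section 8.5 and the synopsis will report ORR with a 95% CI per cohort, and the same estimate and interval would come out if the clause were deleted. A comparison with 17% at the level matching that interval gives the same answer as the interval for 15 to 20 evaluable patients. The only disagreement found, such as 7 of 20, rests on an assumed one-sided 5% level. The 0.424 width is right, it feeds no decision rule, and it does not overstate precision if the EGFR rate is lower. The conclusion assumes that the analysis is carried out as Section 8.5 states and that the interval is the exact one, as the 0.424 implies.

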Once the MTD/MAD is determined, 40 additional NSCLC patients with EGFR (20 patients) or HER2 (20 patients) exon 20 insertion mutations (including duplication mutations) will be enrolled to evaluate the efficacy of pozotinib at the dose and dosing regimen determined in Phase 1. The choice of QD or BID for Phase 2 will be determined by the sponsor and the treatment regimen is selected by the Sponsor. Dose modifications are permitted based on Sponsor recommendations and notification of the Medical Monitor.

During each 28-day cycle, patients who are eligible for participation will receive pozotinib at the assigned dose, orally, QD or BID, depending on the dose identified in Phase 1, continuously. All patients will be treated for up to 24 months or until disease progression, death, intolerable adverse events (AEs), other protocol-specified reasons for patient withdrawal.

Patient Replacement Strategy: Patients in Phase 1 who discontinue from the study before completing Cycle 1 treatment for reasons other than DLTs will be replaced.

Inclusion & Exclusion Criteria:

Inclusion Criteria:

1. Patient is at least 20 years of age
2. Patient must be willing and capable of giving written Informed Consent, adhering to dosing and visit schedules, and meeting all study requirements
3. **Phase 2:** If an archival tissue sample is not available, a tumor biopsy will be required.
4. Previously treated patient with histologically or cytologically confirmed (archival tissue accepted) locally advanced or metastatic non-small cell lung cancer (NSCLC) and is not a candidate for definitive therapy
 - **Phase 1:** No test for mutational status is required
 - **Phase 2:** Documented EGFR or HER2 exon 20 insertion mutation (including duplication mutations) in NSCLC patients. Patients will be enrolled based on documentation of mutational status using PCR or a validated next generation sequencing detection analysis test.
 - Documented *EGFR* exon 20 insertion mutation, including D770_N771insSVD, D770_N771insNPG, V769_D770insASV, H773_V774insNPH, or any other *EGFR* exon 20 in-frame insertion mutation (including duplications).
 - Documented *HER2* exon 20 insertion mutation, including A775_G776insYVMA, G776_V777insVC, or P780_Y781insGSP, or any other *HER2* exon 20 in-frame insertion mutation (including duplications).

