8.3 Analysis Populations

Two analysis populations have been defined for each cohort as follows:

- The **Evaluable Population** consists of all patients in Phase 2 who are enrolled, complete at least 1 cycle of pozotinib treatment, and is evaluable for tumor response based on RECIST, Version 1.1 criteria. The efficacy data will be analyzed using the Evaluable Population.
- The **Safety Analysis Population** includes all patients who signed Informed Consent, enrolled, and received at least 1 dose of pozotinib. All demographics, Baseline characteristics, and safety data will be analyzed using the Safety Analysis Population.

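### The 0.424 confidence-interval width assumes that all 20 enrolled patients per Phase 2 cohort are analysed, but the primary ORR uses the Evaluable Population, so that precision is not assured

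*Combined protocol and SAP*

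**What the plan says.** **Size and precision.** Section 8.1 sets the cohorts by enrolment: "In Phase 2, two cohorts of 20 patients each will be enrolled in previously treated NSCLC patients". It then says: "The above sample size of 20 patients in each mutation cohort will provide a width for 95% confidence interval of 0.424", for an expected ORR of 30%. The synopsis repeats this under Sample Size Justification: "The sample size of 20 patients in each mutation cohort in Phase 2 will provide a width for 95% confidence interval of 0.424". Neither place names the interval method.

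**Role of the figure.** Section 8.1 also says: "Although no a priori test of hypothesis and statistical powering is specified in this study". Section 8.5 says: "The primary endpoint analysis will be performed using point estimate and the 95% CI". The width is therefore the only quantitative support for 20 per cohort.

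**Who is analysed.** Section 8.3 limits the Evaluable Population to enrolled Phase 2 patients who "complete at least 1 cycle of pozotinib treatment, and is evaluable for tumor response based on RECIST", and assigns the efficacy data to that set. Section 8.5 bases ORR on the same set, although its definition of ORR first refers to patients given one or more doses, which is a different denominator.

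**Replacement.** The synopsis rule is confined to Phase 1: "Patients in Phase 1 who discontinue from the study before completing Cycle 1 treatment for reasons other than DLTs will be replaced". Section 8.1 ties replacement to DLT evaluation. Sections 3.1.1 and 8.2 each have a replacement sentence that names no phase, but both stand in Phase 1 text and refer to DLTs. Replacement in Phase 2 is neither provided for nor ruled out.

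**The concern.** The precision statement uses the number enrolled. The primary analysis uses a subset that can only be equal or smaller. One patient who stops during Cycle 1, or who has no usable tumour assessment, takes a cohort below 20.

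The plan foresees drop-out during Cycle 1 in Phase 1 and replaces those patients. Phase 2 makes completion of a cycle a condition for entering the primary analysis, yet has no matching rule and no inflation of the enrolled number. The wording in 8.1 and the synopsis carries no condition on evaluability. What is at stake is whether the one figure that justifies the cohort size describes the analysis that will be reported.

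**Working it through.** **Inputs.** Enrolled per cohort: 20 (8.1). Expected ORR: 30% (8.1), that is 6/20. Confidence level: 95%, taken as two-sided (8.5). Phase 2 non-evaluable rate: not given; losses of 10% and 20% are assumed for illustration.

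**Formula.** For x responders among n analysed, the exact (Clopper-Pearson) limits are

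- lower = 2.5% quantile of Beta(x, n − x + 1)
- upper = 97.5% quantile of Beta(x + 1, n − x)
- width = upper − lower

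**Step 1: reproduce the plan's figure.** x = 6, n = 20: limits 0.1189 and 0.5428, width 0.4239, which rounds to 0.424. Other methods at 6/20 do not match: Wald 0.402, Wald with continuity correction 0.452, Wilson 0.373, Agresti-Coull 0.378, Jeffreys 0.381. The figure is therefore an exact width for 20 analysed patients.

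**Step 2: hold ORR at 30% and reduce n.** The beta quantiles are evaluated at x = 0.3n, which is not a whole number for n below 20. The nearest whole-number case is shown beside it.

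| Analysed n | Width at 30% | Change from 0.424 | Nearest whole-number case |
|---|---|---|---|
| 20 | 0.424 | – | 6/20: 0.424 |
| 19 | 0.435 | +0.011 | 6/19: 0.440 |
| 18 (10% loss, assumed) | 0.446 | +0.022 (5%) | 5/18: 0.438 |
| 17 | 0.459 | +0.035 | 5/17: 0.456 |
| 16 (20% loss, assumed) | 0.472 | +0.048 (11%) | 5/16: 0.476 |

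Percentages: 0.022/0.424 = 5%; 0.048/0.424 = 11%.

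**Step 3: how often a full cohort of 20 would be evaluable.** With independent losses at rate d, the probability is (1 − d)^20. It is 0.95^20 = 36% at d = 5%, 0.90^20 = 12% at 10%, and 0.80^20 = 1% at 20%. These rates are also assumptions.

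**Step 4: variation from the responder count alone.** With nobody lost, 5/20 gives 0.404 and 7/20 gives 0.438. With one patient lost, 5/19 gives 0.421. Averaged over the binomial distribution at a true ORR of 30%, the exact width is 0.413 for n = 20, 0.423 for 19, 0.433 for 18 and 0.457 for 16.

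**The case against.** The strongest reply is that nothing in 8.1 is miscalculated. The figure is a planning value for 20 patients at 30%, and it reproduces. That stands: the defect is an unstated condition, not an arithmetic error.

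A reader might infer that the design fails to provide its stated precision. The documents do not support this. They give no Phase 2 non-evaluable rate, and if all 20 are evaluable and 6 respond, the width is 0.424.

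A reader might also take 0.424 as the most favourable width possible. Step 4 shows otherwise: the realised width depends on the responder count as well as on n, and 5/20 is narrower. Going from 5 to 7 responders among 20 moves the width by 0.034 (0.438 − 0.404), more than the 0.022 attributed to losing two patients at a fixed 30%. The comparison is valid only with ORR held at 30%, which is how 8.1 frames its own figure.

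It is tempting to take an attrition rate from the sponsor's earlier NSCLC study (Section 1.1.3.1), whose per-protocol set kept 35 of 39 patients. Those exclusions were for noncompliance with treatment and a deviation from an inclusion criterion, not for an incomplete first cycle or non-evaluable disease, so they say nothing direct about evaluability here.

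Finally, the absence of a Phase 2 replacement rule is silence rather than a prohibition, and the efficacy analysis is descriptive. Both are true. They limit the weight of the point, but do not remove the mismatch between the number used to justify the size and the number analysed.

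**Conclusion.** The point holds as a mismatch of denominators. The 0.424 belongs to 20 analysed patients at an ORR of 30% with an exact interval. The plan attaches it to 20 enrolled patients, analyses a set that may be smaller, and states neither an attrition allowance nor a Phase 2 replacement rule. The precision is therefore not assured.

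The size is modest: about 0.01 to 0.015 per patient lost, or 5% to 11% wider at an assumed loss of 10% to 20%. This rests on the exact method, which is inferred from the match because the plan does not name it, on ORR fixed at 30%, and on an assumed loss rate. Priority is minor, since no hypothesis test, success criterion or decision rule depends on the width. Any bias in ORR from excluding patients who do not complete a cycle is a separate matter and is not assessed here.

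**What to change.** Either of two edits, made in both 8.1 and the synopsis, is enough.

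1. **Keep the Evaluable Population.** Name the exact (Clopper-Pearson) method, state that 0.424 applies when 20 patients are analysed, and add the width for the number expected to be evaluable: about 0.45 to 0.47 at an ORR of 30% if 16 to 18 of 20 are evaluable. Label the loss rate as an assumption.
2. **Change the denominator.** Make all treated patients the primary ORR denominator, counting those without an evaluable response as non-responders. This agrees with the part of the 8.5 definition that refers to patients given one or more doses. Amend 8.3 and the sentence in 8.5 that names the Evaluable Population, and keep 0.424 with a note that it refers to 20 treated patients.

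No extra patients are needed. The first option costs one sentence in each place and a slightly less favourable stated precision. The second also requires the amendments to 8.3 and 8.5, and removes the conflict between the two denominators in 8.5.
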